6 ANALYSIS SETS

The allocation of subjects to analysis sets will be determined by the sponsor and the CRO on a per-subject basis immediately before data base lock.

Full eligible population (FEP)

The FEP population consists of all screened subjects, both successful and failed screens.

Full included population (FIP)

The FIP population consists of all successful screens.

Safety population (SAF)

The SAF population consists of all patients with a documented MRI/MRA procedure.

Population by country/site (CSP)

The CSP population consists of all successful screens in with known country/site.

Population by GBCA type (GBCAP)

The GBCA population consists of all subjects with known GBCA brand type.

Population by speciality (SPP)

The SPP population consists of all subjects examined for an ailment with known speciality.

Population by GFR rate (GFRP)

The GFR population consists of all subjects with known range of GFR rate.

Population by History of allergy (HISALP)

The history of allergy population consists of all subjects with known history of allergy status.

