1 INTRODUCTION

1.1 Rationale for study

It is currently unknown and of high scientific interest with which dosages the radiologists use the gadolinium-containing contrast media currently available in their market. Such information, which is very important for the referring physicians, can only be obtained by up-to-date observation and documentation in the daily routine.

It is also currently unknown and of further interest for the assessment of the applications, which criteria referrers consider for the administration of gadolinium-containing contrast agents after the publication of the EMA/457616/2017 requirements. In particular, it is unknown whether the presence of pre-existing renal insufficiency is taken into consideration, how often MR contrast agents are used in the same patient and whether this is dependent on indication and/or comorbidities. For example, this question is relevant to patients evaluated for multiple sclerosis and cancers, where it is unknown if notwithstanding the known brain retention of gadolinium, repeated contrast enhanced MR scans are considered necessary. Also, it is unknown if dose reductions, perhaps dependent on scanner magnetic field strength, are applied.

The study plan/protocol and the resulting documentation sheet of the requested study accurately collects data useful to clarify these points and will therefore provide more accurate insight into the potentially adapted clinical procedure.

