3.2.1.3 Medical summary

- Diagnosis to which MR scan has been indicated
- Question to be answered with the use of CE-MR
- Secondary diagnosis
- Reason for using a contrast medium (border delineation of pathology, overall morphological characterization of pathology/lesion, overall increase in resolution of images required, confirmation of opinion/diagnosis, for comparison with non-contrast enhanced images, angiography or myocardial assessment, standard procedure for this diagnostic question, other)
- Specific reason why the GBCA was used
- Comorbidities (none, allergy, diabetes mellitus, heart failure, hepatic impairment, hypertension, neurologic symptom, renal impairment, autoimmune disease, malignancy/cancer, other)
 - Allergy status for patients with allergies (bronchial asthma, eczema, food allergy, urticaria, previous history of allergy to other contrast media [unknown media, Iodine-based media, Gadolinium-based media, ultrasound media, other media])
 - Renal status eGFR for patients with renal impairment (< 15, 15-30, 31-60, > 60 mL/min/m², impaired [exact eGFR unknown], unimpaired [exact eGFR n/a])
 - If renal status < 60 mL/min/m²: status of renal replacement for the compromised kidney(s) (renal replacement – dialysis, renal transplant, no replacement)
- Pre-medications (none, steroids, anti-histamines, other)
- Concomitant medications (no co-medication, chemotherapy/active treatment for malignancy, radiotherapy, anti-hypertensives, diabetic medications, heart failure treatment, nephrotoxic medication [antibiotics, iodinated agents, oncological drugs, immunosuppressants, other], other)
- Source of funding for the scan (self-funded [n/a, full, partially], paid by personal/hospital insurance, reimbursed by the state)

- If funding = insurance or reimbursed, what is being paid for (contrast media, procedure, procedure including contrast media)

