7.1.4 Medical history

The number and frequency of comorbidities, pre-medications, concomitant medications and patients with previous scans will be analysed for all patients (FIP) and by GBCA (GBCAP). Additionally, number and frequency of previous scans will be shown by site (SPP) and by country (CSP). For patients with allergies, further details about the allergy status will be tabulated. For patients with renal impairment eGFR and the renal replacement status will be analysed.

A patient is defined to have a previous scan if either the referral type is a repeat scan or any other image scan has been performed before the contrast enhanced MR scan session in relation to the illness under investigation.

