7.1.7 Injection and scanning

The volume of contrast agent, the volume of saline follow-up injection and the dose, the number and frequency of injector usage, the sequence type (standard vs modified, coded specific sequence type), the reason for modified sequence will be analysed for all patients (FIP), by site (CSP), by country (CSP), by specialty (SPP), by GBCA (GBCAP), by scanner type (FIP), by scanner field strength (FIP) and by scan modality (MRA/MRI).

The sequence type will additionally be analysed by injection protocol for all patients (FIP), by site (CSP), by weight (FIP) and by country (CSP).

The mean volume of contrast agent and the volume of saline follow-up injection will be shown in a bar chart for type of sequence.

The dose in mmol/kg will be calculated according to

$$\text{Dose} = \text{injected volume} * \text{GBCA concentration} / \text{weight}$$

Where GBCA concentration = 1 mmol/mL for Gadovist and
 0.5 mmol/mL for all other GBCA

Dose will also be analysed for the following categorisation:

≤0.1, > 0.1 to 0.2, > 0.2 to 0.3 and >0.3 mmol/kg

for all patients (FIP), by GBCA (GBCAP), by age groups (FIP), by GFR rate (GFRP), and by indication (see 3.2.1.5).

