7.3 Adverse events

Analysis of safety will be based on the safety population (SAF).

The number and frequency of patients with adverse events and serious adverse events will be analysed overall, by age group (SAF), by history of allergy (HISALP), by GFR rate (GFRP), by site (CSP) by country (CSP), by specialty (SPP) and by GBCA (GBCAP) by MedDRA SOC and PT.

The number and frequency of adverse events will also be analysed for the subgroups given above stratified by causality, treatment, severity and onset of the adverse event.

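### The dose-by-GFR and adverse-event-by-GFR tables use a set with an undefined entry rule and a contradictory source field, so they may lack a normal-function group and an eGFR-unknown row

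*SAP*

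**What the plan says.** Section 6 sets the entry rule for the GFR population (GFRP): "The GFR population consists of all subjects with known range of GFR rate". It does not list which recorded options count as a known range.

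The source item is in Section 3.2.1.3, nested under comorbidities and introduced as "Renal status eGFR for patients with renal impairment". It has six options. Four are numeric bands (below 15, 15-30, 31-60, above 60). The other two carry no band: "impaired [exact eGFR unknown], unimpaired [exact eGFR n/a". Section 7.1.4 repeats the restriction in the label: "For patients with renal impairment eGFR and the renal replacement status will be analysed".

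Two planned analyses use GFRP. Section 7.1.7 tabulates categorised dose "by GFR rate (GFRP), and by indication" (Table 7.20), and Section 7.3 tabulates adverse events and serious adverse events by the same grouping (Table 11.6.2). Section 5.5 rules out replacing missing values, and Section 7 bases percentages on the non-missing count.

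The rationale in Section 1.1 says that "it is unknown whether the presence of pre-existing renal insufficiency is taken into consideration".

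**The concern.** To learn whether renal insufficiency influences practice, one needs dose in patients with impaired function set against dose in patients without it. One also needs the share of patients given contrast whose renal function was not known. The same reference group is needed to interpret adverse events by renal status. If GFRP follows its wording, the two tables meant to carry this information may contain only degrees of impairment among patients already flagged, with neither group present.

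Section 7 also allows exploratory chi-square tests across strata, and Section 5.8 declares p below 0.05 significant. A p-value by GFR could therefore come from flagged patients alone, and nothing planned for the table would tell the reader so. Section 6 leaves allocation to analysis sets until just before database lock, patient by patient, so the meaning of a known range could be settled with the data in hand.

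**Working it through.** The SAP states no size for GFRP and no prevalence of renal impairment, so there is no figure to reproduce. The check sets Section 3.2.1.3 (label and options) and Section 7.1.4 against the Section 6 rule, under the readings that the text allows.

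| Recorded status | A: field completed only for flagged patients; numeric band required | B: field open to all; numeric band required | C: field open to all; any classification counts as known |
|---|---|---|---|
| <15, 15-30, 31-60 | in | in | in |
| >60 | in, but only patients flagged as impaired | in, only patients with a band recorded | in |
| Impaired, eGFR unknown | out | out | in |
| Unimpaired, eGFR n/a | out | out | in |
| Impairment not ticked, field blank | out | out | out |

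**Reading A** follows the label in Section 3.2.1.3 and its echo in Section 7.1.4. Tables 7.20 and 11.6.2 have no normal-function group, because even the band above 60 consists of patients flagged as impaired.

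**Reading B** follows the option list, since above 60 and unimpaired make little sense in an item meant for impaired patients only. The band above 60 can then serve as a reference, but it holds only patients with a band recorded. Patients classed as unimpaired without a value, and those impaired with eGFR unknown, are still outside.

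**Reading C** brings both of those groups in, but it requires treating an option without a band as a known range, and the SAP does not say so.

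Illustrative sizes, using the planned maximum of 5400 (Section 3.1):

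- Reading A: size is at most 5400 × p, where p is the proportion flagged as impaired. The SAP gives no p. For assumed values of 2%, 10% and 20%: 5400 × 0.02 = 108; 5400 × 0.10 = 540; 5400 × 0.20 = 1080. These are upper limits, because flagged patients with eGFR unknown also drop out.
- Reading B: the number with a numeric band, which the SAP does not allow one to bound.
- Reading C: up to 5400 if the field is completed for everyone.

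Where the excluded patients would still be seen:

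- Tables 1.1 to 1.3 cover disposition and analysis populations, so the size of GFRP may appear beside the full included population (FIP).
- Section 7.1.4 reports comorbidities for all patients and by GBCA, and eGFR for impaired patients. The impaired-with-eGFR-unknown response is a recorded answer, so the non-missing denominator does not remove it there.
- The overall dose tables (FIP) and overall adverse-event tables (safety population, SAF) include these patients whatever their renal status.

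None of these tables crosses dose or adverse events with impaired against not impaired. Only the by-GFR tables do anything of the kind, and they use GFRP.

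**The case against.** The strongest reply is that the option list shows the field was open to everyone. An item offering above 60 and unimpaired is not an impaired-only item, and lacking an exact eGFR is not the same as being unclassified. If so, the reference group is inside GFRP and the label is merely careless. This is a fair reading, and it rules out saying as fact that eGFR was recorded only in impaired patients or that no unimpaired comparison exists. It does not clear the plan: Section 7.1.4 repeats the restriction in the label, and Section 6 asks for a known range, which two of the six options do not supply.

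A second reply is that nobody is concealed. That stands. A reader might infer that untested patients vanish from the report, but the overall FIP and SAF tables keep them, and the population and medical-history tables probably show their number. The gap is confined to Tables 7.20 and 11.6.2.

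A third reply is that the study is descriptive, tests no prior hypothesis, and treats GFR as one of many strata. That also stands, and it limits the severity. Renal insufficiency is nonetheless one of the few questions that the rationale names, and these are the tables that bear on it.

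**Conclusion.** The SAP contradicts itself on who has renal status recorded and does not define which options count as a known range. On the literal reading, Tables 7.20 and 11.6.2 lack a normal-function group and a row for unknown renal function. If the field was open to all, they still omit the two options without a numeric band unless the definition is widened. GFRP could hold a few percent of patients or nearly all 5400. No single figure can be defended, because the lower end rests on an assumed prevalence and on the literal reading.

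This should be fixed, but it does not threaten the main description of GBCA use. A reader might extend the point to the history-of-allergy population. The document does not support that: the set requires a known allergy status, and the comorbidity list offers a none option, so a patient without allergy can already belong to it.

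**What to change.** - Reconcile Sections 3.2.1.3, 6 and 7.1.4: state whether renal status is recorded for every patient or only for those flagged as impaired.
- Base Table 7.20 on the FIP and Table 11.6.2 on the SAF, with one row for each of: <15; 15-30; 31-60; >60; impaired with eGFR unknown; unimpaired with eGFR n/a; renal impairment not ticked; missing. Give counts and percentages on the full denominator, as a stated exception to the non-missing rule in Section 7.
- Add a comparison of impaired with not impaired for dose and for adverse events.
- Keep the not-ticked group as its own row, since an unticked box is weaker evidence of normal function than a recorded classification.
- If eGFR proves to exist only for flagged patients, say in the titles of any tables by eGFR band that those bands describe impaired patients only.

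The cost is a SAP amendment and one derived variable from fields already listed for collection; no new data are needed. The drawback is some less certain or sparse rows, which separate display makes visible. The change is best made before any by-GFR table is run, including for the interim analysis in Section 5.2.

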7 STATISTICAL METHODS

All continuous variables will be summarized using the following descriptive statistics: n (non-missing sample size), mean, standard deviation, median, minimum and maximum. The frequency and percentages (based on the non-missing sample size) will be reported for categorical measures. Data that will be listed will be sorted by country, site and subject.

For the comparison of endpoints in stratified analyses (e.g. by country, by GBCA etc.) explorative statistical tests will be applied (ANOVA for continuous endpoints, Chi-Square tests for categorical endpoints) if feasible.

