1.2 Purpose of the analyses

The study is set-up for descriptive purposes, no a priori hypothesis will be tested.

The statistical analysis plan (SAP) is a more detailed description of the statistical rationale and the methods used for generating the results of this observational study.

It contains additional information not covered by the study protocol (Version 1.5, 28-Nov-2018).

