3 STUDY METHODS

3.1 Study design and plan description

This is a prospective, multi-center observational study.

It is planned to enroll up to 5400 patients from 7 countries and 14 sites.

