3.2.3 Centre data

- Number of available scanners in centre (MRI, CT, ultrasound, PET-PET/CT, PET/MR, SPECT, X-ray)
- Number of procedures performed in the centre (liver-specific MR, Non_CE MR, CE-MRI, CE-MRA, CT, ultrasound, PET-PET/CT-PET/MR, SPECT, X-ray, other) during the study period
- Number of staff members (radiologists, radiographers, nurses)
- Decision for use of a specific contrast medium (individual decision, collective decision)
- Decision maker for use of specific contrast medium (Head of radiology department, radiologist, specialty physician, pharmacist, manager [non-clinician], other)
- Challenges faced by radiology department
- User satisfaction with GBCA packaging and injectors
 - for each GBCA
 - Satisfaction with GBCA packaging (could be improved, o.k., excellent/particularly good)
 - Satisfaction with injector (could be improved, o.k., excellent/particularly good)

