5.6 Multi-center studies

Not applicable

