5.7 Multiple testing

Due to the explorative design of the observational study there will be no adjustments for multiple statistical tests.

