5.8 Statistical significance (p-values)

A p-value of <0.05 will be declared as statistically significant.

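### Site clustering is set aside as not applicable in a 14-site study, so country p-values, and brand or scanner p-values where these factors cluster by site, can be far too small

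*SAP*

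**What the plan says.** SAP section 3.1 describes the design: "This is a prospective, multi-center observational study", and "It is planned to enroll up to 5400 patients from 7 countries and 14 sites". The SAP has a place for the handling of centres, headed "5.6 Multi-center studies", and its whole entry is that this is not applicable.

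Section 5.3 lists site as one stratification factor beside specialty, country, GBCA type, scanner type, field strength and scan modality. Section 7 says that, for stratified comparisons such as by country or by GBCA, "explorative statistical tests will be applied (ANOVA for continuous endpoints, Chi-Square tests for categorical endpoints) if feasible". Neither section puts a site term, a random effect, a cluster-robust variance or a site-stratified test into these comparisons.

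On interpretation, section 1.2 states that "no a priori hypothesis will be tested". Section 5.7 adds that "there will be no adjustments for multiple statistical tests", and section 5.8 that "A p-value of <0.05 will be declared as statistically significant".

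Section 3.2.3 collects, on the centre form, "Decision for use of a specific contrast medium (individual decision, collective decision", together with who the decision maker is.

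**The concern.** Ordinary ANOVA and the Pearson chi-square test assume independent patients. Patients at one site share radiologists, scanners, injection habits and image readers, so their doses, image-quality ratings and confidence scores are likely to be correlated.

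The effect on a p-value depends on how the compared factor lies across sites. Country is made up of whole sites, so a country comparison is clustered by construction. Brand, scanner make and field strength are clustered to the extent that each site tends to use one or a few of them. A table by site does not help, because the country and brand tests remain pooled over sites.

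Dose, image quality, diagnostic impact and adverse events are all tabulated by GBCA (sections 7.1.7, 7.1.8 and 7.3), and the primary objective makes special reference to one product. A difference in local habit could therefore be reported as a statistically significant difference between products or countries.

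**Working it through.** The SAP states no power, ICC or error figure, so there is nothing of its own to reproduce. The check asks how often the planned test rejects when no true country or brand difference exists.

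**Inputs from the SAP:** N = 5400, 14 sites, 7 countries (section 3.1); significance at 0.05 (5.8); ANOVA or chi-square on patients (7).

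**Assumptions:** equal sites, two sites per country, a continuous endpoint, and an ICC of 0.001 to 0.05.

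**Cluster size:** m = 5400/14 = 385.7.

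**Design effect:** DE = 1 + (m − 1) × ICC. **Effective N** = 5400/DE.

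**Two brands, each used by 7 whole sites:** true error ≈ 2 × [1 − Φ(1.96/√DE)]. At ICC 0.01, 1.96/√4.85 = 0.89, which gives 37%.

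**Seven countries of two sites:** the between-country statistic has 6 df and is inflated by DE, so true error ≈ Pr(χ²₆ > 12.59/DE). At ICC 0.01, 12.59/4.85 = 2.60, which gives 86%.

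| ICC | DE | Effective N | Two brands: formula (simulated) | Country: formula (simulated) |
|---|---|---|---|---|
| 0.001 | 1.38 | 3900 | 10% (10%) | 17% (16%) |
| 0.01 | 4.85 | 1114 | 37% (38%) | 86% (85%) |
| 0.05 | 20.2 | 267 | 66% (66%) | 99.6% (99.5%) |

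The simulations used 3,000 runs per setting. A separate set of 20,000 runs gave 37.4% and 66.7% for two brands, and 86.2% and 99.6% for country, at ICC 0.01 and 0.05. At ICC 0 the planned test was correct (4.7% for country, 4.8% for two brands). Unequal site sizes (coefficient of variation 0.6) raised the two-brand figure at ICC 0.01 to 40%.

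**Brands mixed within sites, ICC 0.05,** by the assumed share of brand variance lying between sites:

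| Share between sites | True error of planned test |
|---|---|
| 0 (same mix at every site) | 4.7% |
| 5% | 15% |
| 20% | 35% |
| 50% | 53% |
| 80% | 63% |

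**With site accounted for:** ANOVA on site means rejected in 4.4% to 6.6% of runs across the country and brand layouts. A site-stratified brand comparison with mixed brands rejected in 4.3% to 5.5%. Both are close to the nominal 5%.

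**Degrees of freedom for country at site level:** 7 − 1 = 6 between countries and 14 − 7 = 7 between sites within countries.

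**The case against.** The best defence is that the study is descriptive and its tests are labelled exploratory and run only where feasible. The primary objective is pattern of use. The planned means, standard deviations, medians, ranges and percentages do not depend on the choice of test, and no confidence intervals are planned. All of that stands and limits the harm to the p-values. It does not repair them. An exploratory label can excuse the lack of multiplicity adjustment, but it does not correct a wrong variance, and section 5.8 still attaches a significance verdict.

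A second defence is that brand may vary freely within sites. Section 3.2.3 only asks whether the choice is individual or collective, and satisfaction is recorded for each GBCA, which allows several brands per centre. Brand, scanner make and field strength are recorded per examination (3.2.1.5). This also stands: the SAP does not establish that brand is set by site, and the two-brand figures in the first table are the extreme case.

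A reader might infer that most significant brand or country differences will be site effects. The SAP does not support that. The false share of significant results is (1 − p)a/[(1 − p)a + 0.9p], where a is the true error rate, p the share of differences that are real, and 0.9 an assumed power. With a = 0.40 and p = 0.75 it is 0.10/0.775 = 13%. With a = 0.70 and p = 0.10 it is 0.63/0.72 = 88%. The SAP fixes neither a nor p.

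Nor can the number of false positives be counted from Appendix 1, which does not say which tables carry tests. Those tests would not be independent either.

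**Conclusion.** The point holds in a bounded form. The SAP contradicts itself by describing a multi-centre study and then setting centre handling aside, and its named tests ignore the site structure.

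For country the problem follows from the design, and even an ICC of 0.001 roughly triples the nominal error. For brand, scanner make and field strength the size depends on how far each follows site. It can be large, or absent if the mix is the same everywhere. Tests between sites are sound, because site is then the factor of interest.

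The direction rests on the SAP alone. The percentages rest on the assumed ICC range, equal site sizes, two sites per country and the stated brand layouts.

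**What to change.** Replace the entry in 5.6. Comparisons by GBCA, scanner type, field strength and specialty should account for site, through a site effect in the model or through site-stratified or cluster-robust tests. With only 14 clusters, random-effect and cluster-robust methods need a small-sample correction. Report differences with 95% confidence intervals where feasible. Sparse adverse-event tables may not support a model. Adjusting for indication or age group is an option, not a requirement of this point.

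State that brand cannot be separated from site where a site uses only one brand. A random intercept would then widen the interval without removing the confounding. A table of brand by site would show how far this applies.

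For country, use a site-level test (about 6 and 7 df) or give the tables without p-values. A fixed site effect would absorb country and cannot be used there.

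Delete the significance declaration in 5.8 and call the remaining p-values descriptive, in line with 1.2. The minimum alternative is to drop the brand and country p-values altogether.

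The cost is SAP wording and some extra programming, with wider intervals and fewer results called significant. The minimum alternative costs almost nothing.
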